- high-grade intraepithelial lesion (HSIL),
- atypical glandular cells (AGC) or epithelial cell abnormality,
- cervical intraepithelial neoplasia grade 2 (CIN 2) (on cervical biopsy),
- cervical intraepithelial neoplasia grade 3 (CIN 3) (on cervical biopsy).

For any atypical finding that can be treated, please contact the AbbVie TA MD to determine if the subject may remain in screening and can be eligible for randomization.

During the Treatment Period, if the Pap Test performed at Month 24 and/or Month 48 indicates a clinically significant finding in the opinion of the investigator and requires additional testing (e.g., colposcopy or biopsy) as follow-up, the AbbVie TA MD should be notified for additional guidance and approval. A Pap Test is not required at PD if one was performed within approximately six months prior to the PD visit.

COVID-19 Pandemic-Related Acceptable Protocol Modifications

Due to the COVID-19 pandemic, if the subject is unable to complete the Pap Test at its scheduled time, it can be delayed up to one month. Should the delay be longer, AbbVie should be notified for further guidance.

Clinical Laboratory Tests

Samples will be obtained for the laboratory tests listed in Table 4, at the time points indicated in Appendix C.

Table 4. Clinical Laboratory Tests

Hematology	Clinical Chemistry (After Minimum 8-Hour Fast)	Urinalysis
Hematocrit Hemoglobin Red Blood Cell (RBC) count White Blood Cell (WBC) count Neutrophils Bands (if indicated) Lymphocytes Monocytes Basophils (if indicated) Eosinophils (if indicated) Platelet count (estimate not acceptable) Mean Cell Volume of RBC (MCV) Mean Corpuscular Hemoglobin (MCH) Mean Corpuscular Hemoglobin Concentration (MCHC) Pregnancy Test Serum pregnancy	Sodium Potassium Chloride Bicarbonate Blood Urea Nitrogen (BUN) Serum creatinine Glucose Calcium Total protein Albumin Total bilirubin Serum glutamic-pyruvic transaminase (SGPT/ALT) Serum glutamic-oxaloacetic transaminase (SGOT/AST) Alkaline phosphatase Vitamin D	Specific gravity Ketones Protein Blood Glucose pH Lipid Panel (After Minimum 8-Hour Fast) Low-density Lipoprotein (LDL) cholesterol High-density Lipoprotein (HDL) cholesterol Total cholesterol Triglycerides Endocrine Panel Follicle-stimulating hormone (FSH) Reflexive Thyroid Stimulating Hormone (TSH)

Laboratory samples indicated in Table 4 will be assessed using a certified central laboratory selected for the study and these data will be used for data analysis. The central

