subject cannot return to the site within 28 days (1 month), the AbbVie TA MD should be contacted for additional guidance.

Study drug administration may be continued provided the investigator has reviewed all prior laboratory results and confirms and discusses with the subject that there are no safety concerns for the subject to continue use of the study drug in the absence of current labs. If the Investigator has questions about the subject's historical lab results and/or the subject's continued eligibility, the AbbVie TA MD should be consulted.

Lipid Panel

Serum lipids consist of LDL cholesterol, HDL cholesterol, triglycerides and total cholesterol; non-HDL cholesterol and lipid ratios will also be calculated, but will not be reported to the investigative site.

[figure not shown]
The lipid panel samples should be obtained in the morning following an overnight fast (minimum of 8 hours); however, there may be circumstances when a sample is obtained later in the day and/or not under fasting conditions. If a sample was obtained after less than 8 hours of fasting, the source documents and the lab requisition should be marked to indicate that the sample was obtained under non-fasting conditions.

Endocrine Panel

The endocrine panel consists of the following analytes: serum FSH and reflexive TSH. Reflexive TSH will be obtained at Screening only.

Optional Testing for Gonorrhea and Chlamydia

Gonorrhea and chlamydia testing can be ordered at the Investigator's discretion during the Screening and Treatment Periods, to test for active gonorrhea or chlamydia prior to performing the endometrial biopsy. These samples will be sent to the central laboratory for analysis. If the Investigator determines that an abnormal test result can be treated, treatment will be outside of the protocol. Follow-up chlamydia/gonorrhea testing (per

instructions from the central lab) can be performed after treatment at the Investigator's discretion.

Serology Screening for Hepatitis and HIV

Samples will be tested for HAV-IgM, HBsAg, HCV Ab, HIV Ag/anti-HIV Ab by the central laboratory for all subjects during the Screening Period. If any of these tests are positive or reactive, the subject is excluded from study participation. Borderline hepatitis test results should be repeated.

The results of the HIV Ag/anti-HIV Ab testing will be retained confidentially by the study site.

Electronic Daily Diary (e-Diary)

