8.1.7.3 Analysis of Laboratory Data and Vital Signs

Changes from the baseline to each visit in continuous laboratory and vital sign parameters will be summarized by treatment group. Treatment group differences for changes from

baseline during the first 12 months of the treatment period will be analyzed using a one-way ANOVA with treatment as the main effect.

Laboratory values will be categorized as low, normal or high based on normal ranges of the central laboratory used in this study. Low or high laboratory values will be flagged in the data listings.

The number of subjects reaching potentially clinically significant levels will be summarized by treatment group. Criteria will be summarized by treatment group.

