9.3 Analysis of Laboratory Data

Data collected from central and local laboratories, including additional laboratory testing due to an SAE, will be used in all analyses, except for Baseline where SAE-related laboratory assessments on or before the first dose of study drug will be excluded. The clinical laboratory tests defined in the protocol operations manual (i.e., hematology and clinical chemistry) will be summarized.

Each laboratory variable will be summarized for all time points (starting with Baseline) with the number of non-missing observations, mean and standard deviation, median, minimum and maximum. Mean change from baseline to each applicable post-baseline visit will be summarized for selected laboratory variables, with the number of observations, baseline mean, and visit mean. The change from baseline mean, standard error, and 95% confidence interval will be presented for the mean change from baseline within each treatment group and difference between each elagolix group and placebo. Selected laboratory variables are lipid variables, liver variables (alkaline phosphatase, ALT, AST, bilirubin), hemoglobin, hematocrit, platelet count, and red blood cell (RBC) count. For lipid variables, in addition to low-density lipoprotein cholesterol (LDL-C), high-density lipoprotein cholesterol (HDL-C), total cholesterol, triglycerides (TG) and apolipoprotein A and B, the following ratios will be included: the ratio of total cholesterol to HDL-C, the ratio of LDL-C to HDL-C, the ratio of TG to HDL-C, and the ratio of non-HDL-C (calculated as total cholesterol minus HDL-C) to HDL-C.

Changes in selected laboratory parameters will be tabulated using shift tables by NCI CTC criteria and categorized as low, normal, or high based on the normal ranges of the laboratory used for each sample. A shift table from baseline either to the worse value (based on NCI CTC criteria) during treatment or to minimum and maximum value (based on normal range), will be created. A similar shift table will be provided to summarize shifts from baseline to the final post-baseline value.

Laboratory abnormalities meeting CTC criteria grade 3 or 4 will be summarized.

The number and percentage of subjects meeting the following sponsor-defined potentially clinically significant lipid values will be summarized at baseline and each relevant visit by treatment group in the appropriate Treatment Period:

- Total cholesterol: ≤ 300 , $> 300 - \leq 400$, $> 400 - \leq 500$, and > 500 mg/dL

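### SAP 9.3 admits local and SAE-triggered laboratory values to every post-baseline analysis, against the protocol's central-laboratory rule, and gives no rule for non-fasting lipid samples

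*SAP*

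**What the plan says.** **Source of data.** Protocol 5.3.1.1 (Clinical Laboratory Tests) says that the Table 4 samples "will be assessed using a certified central laboratory selected for the study and these data will be used for data analysis", and that all clinical laboratory samples are shipped to the central laboratory. SAP 9.3 says: "Data collected from central and local laboratories, including additional laboratory testing due to an SAE, will be used in all analyses, except for Baseline". The exception covers SAE-related results at or before first dose and nothing else.

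**Reference ranges.** Protocol 8.1.7.3: "Laboratory values will be categorized as low, normal or high based on normal ranges of the central laboratory used in this study". SAP 9.3 has values "categorized as low, normal, or high based on the normal ranges of the laboratory used for each sample".

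**Outputs fed by these data.** SAP 9.3 plans visit summaries, mean change from baseline within each group and as a difference from placebo (with 95% confidence intervals), and plots of means over time. It also plans shift tables to worst and final values, CTC grade 3 or 4 tables, lipid bands by visit, counts of potentially clinically significant (PCS) lipid values at any time, and hepatotoxicity tables based on maxima.

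**Fasting.** The Lipid Panel text in Protocol 5.3.1.1 asks for a fast of at least 8 hours but accepts that some samples will be non-fasting. For those, "the source documents and the lab requisition should be marked to indicate that the sample was obtained under non-fasting conditions". SAP 9.3 does not mention fasting.

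**Lipid analytes.** Protocol 5.3.1.1: "Serum lipids consist of LDL cholesterol, HDL cholesterol, triglycerides and total cholesterol". SAP 9.3 adds apolipoprotein A and B to the mean-change summaries and to the plots.

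**The concern.** SAE-triggered tests are done because something has happened to the patient. Removing them from Baseline concedes that they do not represent her usual state, yet the same kind of value is allowed into every post-baseline mean. Worst-value tables should include such results. Visit means and differences from placebo should not, because whether the extra value exists depends on the outcome. If one arm has more SAE testing, its mean change moves for a reason unrelated to the scheduled course of the analyte.

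The plan also leaves the choice of value open. SAP 9.5.2 says which value to take when several bone density scans fall in one window, and SAP 9.5.7 says what to do with several biopsies. SAP 9.3 has no such rule, so two analysts could produce different visit means from the same data.

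For triglycerides, the protocol has sites mark non-fasting samples, but the SAP does not use the mark. With no exclusion, these samples enter the triglyceride means, bands and PCS counts. Lipid and liver changes against placebo are important safety outputs for a regimen containing an estrogen and a progestin.

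**Working it through.** The documents give no figure for this point, so there is nothing to reproduce. The conflict is textual. The sizes below rest on assumptions.

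**1. The texts side by side**

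| Item | Protocol | SAP 9.3 |
|---|---|---|
| Source | Central laboratory | Central and local, including SAE testing |
| Ranges | Central laboratory | Laboratory used for each sample |
| SAE values before or at first dose | Not addressed | Excluded from Baseline |
| SAE values after first dose | Not addressed | Included in all analyses |
| Several values in one window | Not addressed | No rule |
| Non-fasting lipids | Must be marked | Not mentioned |
| Apolipoproteins A and B | Not in Table 4 or the lipid panel | Summarised and plotted |

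**2. How far event-driven values could move a mean**

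Assume that a share g of an arm has its visit value replaced by one D standard deviations more abnormal. The arm mean then moves by g × D.

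- Low end: g = 0.5%, D = 1 gives 0.005 × 1 = 0.005 SD.
- Middle: g = 2%, D = 2 gives 0.02 × 2 = 0.04 SD.
- High end: g = 5%, D = 4 gives 0.05 × 4 = 0.20 SD.

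With the planned 400 and 200 subjects, the standard error of the difference is √(1/400 + 1/200) = 0.087 SD. The bias in the difference is (g × D) in one arm minus (g × D) in the other, so it is zero when the two are equal. In the extreme case of 0.20 SD in one arm and none in the other, it is 0.20 / 0.087 = 2.3 standard errors.

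**3. Non-fasting samples and triglycerides above 150 mg/dL**

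*One visit.* Assume a lognormal distribution with fasting median 90 mg/dL and log SD 0.45. All fasting: 1 − Φ((ln 150 − ln 90)/0.45) = 12.8%. Now let 2–20% of samples be non-fasting, with values 10–30% higher. At the high end, the non-fasting median is 117 mg/dL and the exceedance is 29.0%, so the mixture is 0.80 × 12.8% + 0.20 × 29.0% = 16.1%. The low end gives 12.9%.

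*Any value in the blinded period.* Appendix C schedules post-baseline lipid panels at Months 6 and 12. Assume log triglyceride = ln 90 + a between-woman term (SD 0.40) + a within-woman term (SD 0.20), and multiply a share f of samples by m. The probability that at least one of two samples exceeds 150 mg/dL is 1 − E[(1 − q)²], where q is a woman's own per-sample probability:

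| f | m | Any value > 150 mg/dL |
|---|---|---|
| 0 | – | 18% |
| 10% | 1.15 | 19% |
| 20% | 1.30 | 23% |
| 30% | 1.30 | 25% |

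*Difference between arms.* Take the one-visit model with equal non-fasting shares and an assumed 10% drug effect on the median (99 versus 90 mg/dL). The difference in proportions is 4.98 points when all samples are fasting, and 5.00 to 5.51 points with 2–20% non-fasting.

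**The case against.** The protocol says that central data will be used, not that only they will be, and it defers analysis details to the SAP. Scheduled samples go to the central laboratory, so local values would be additions to that series. Ranges matched to each sample's laboratory deal reasonably with local results in low/normal/high tables. Excluding pre-dose SAE values from Baseline is sensible and applies to every arm. All of this stands, but none of it says which value enters a visit mean, and the words covering all analyses contain no exception for means or placebo differences.

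Four stronger readings are tempting, and the documents do not support them.

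- *Mean changes are tilted and triglyceride counts are inflated.* The documents give no frequency of local, SAE-triggered or non-fasting values, so only the possibility is shown. The fasting gap is an omission, because the SAP sentence on data sources says nothing about fasting. The SAP does not call its triglyceride cut-offs fasting limits. Non-fasting samples on Day 1 could also partly offset change from baseline.
- *Non-fasting samples dilute the contrast with placebo.* With equal shares in each arm, the calculation shows the difference in proportions growing slightly.
- *The count up to Month 48 is the relevant one.* Over 12 lipid visits the same model gives 33% rising to 35–46%. SAP 9.3 counts within the appropriate Treatment Period, and SAP 9.1 separates the blinded and open-label periods. A count over all 12 visits fits only the All Elagolix plus E2/NETA set, where no comparison is made by default.
- *Apolipoproteins cannot be derived.* SAP 9.3 takes its tests from an operations manual that was not available, and the SAP (May 2020) predates this protocol amendment (April 2022). All that can be said is that the protocol lists do not include them.

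**Conclusion.** The point holds as a conflict between SAP 9.3 and the protocol, with a missing selection rule. As written, SAP 9.3 lets event-driven values into post-baseline visit means, mean changes and differences from placebo. The differences are biased if SAE testing, or how abnormal its results are, differs by arm. On assumed inputs the effect runs from negligible to more than two standard errors, and the documents cannot narrow that range. Pooling all sources remains appropriate for worst-case tables.

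The silence on non-fasting samples is a separate, smaller gap. It can raise triglyceride counts in all arms (about 18% to 19–25% over the two blinded-period samples, on assumed inputs), with little effect on a comparison if the shares are alike. The apolipoprotein item is a reconciliation only. No efficacy conclusion is touched. The change should be made because it affects placebo-controlled safety comparisons and costs little.

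**What to change.** In SAP 9.3:

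1. Compute visit means, changes from baseline and differences from placebo from protocol-scheduled central-laboratory samples. State which value is used when several fall in one window.
2. Keep local and SAE-driven values for the worst-value, shift, CTC-grade, any-time PCS and hepatotoxicity tables, and say that this departs from the central-only wording of Protocol 5.3.1.1 and 8.1.7.3. For final-value shifts, state whether an SAE-driven result may serve as the final value.
3. Base triglyceride and TG/HDL-C summaries, including their PCS counts, on samples not marked non-fasting, with all samples as a sensitivity analysis. First confirm that the mark reaches the laboratory dataset, because the protocol places it only in source documents and on the requisition. Say how local results without any fasting information are treated.
4. Cite where apolipoprotein A and B are collected, or drop those outputs.

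The cost is SAP wording and filters on laboratory source, visit and, if available, fasting status. The main tables would contain slightly fewer values. No new data collection is needed if the fasting mark is already transferred.

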- 10. Subject is unable or unwilling to discontinue use of any prior analysis on entry into the Screening Period or if a subject has a clinically significant sensitivity, allergy to, or any other reason that in the Investigators opinion that would prevent the subject from using all of the protocol allowed rescue analysis medications.

- 11. Subject is unable or unwilling to discontinue use of medical treatments for endometriosis on entry into the Washout or Screening Period.
- 12. Subject has chronic pelvic pain that is not caused by endometriosis (e.g., interstitial cystitis, adenomyosis [as a dominant condition diagnosed by MRI or ultrasound], fibroids, pelvic inflammatory disease [PID], non-endometriosis-related pelvic adhesive disease, irritable bowel syndrome), that requires chronic analgesic therapy, which would interfere with the assessment of endometriosis-related pain.
- 13. Subject has any other chronic pain syndrome (e.g., fibromyalgia, chronic back pain, myofascial pain syndrome, chronic headaches) that requires chronic analgesic or other chronic therapy, which, in the opinion of the Investigator, would interfere with the assessment of endometriosis-related pain.
- 14. Subject is using any systemic corticosteroids for over 14 days within 3 months prior to Screening or is likely to require treatment with systemic corticosteroids during the course of the study. Over-the-counter and prescription topical, inhaled or intranasal corticosteroids are allowed.
- 15. Subject has any of the following:
 - Major depression or a post-traumatic stress disorder (PTSD) episode within
 2 years of the Screening visit
 - Other major psychiatric disorder at any time (e.g., schizophrenia, bipolar disorder)
- 16. Subject has a history of suicide attempts or answered "yes" to questions 4 or 5 on the suicidal ideation portion of the Columbia-Suicide Severity Rating Scale (C-SSRS) within the last 1 year at Screening or Day 1, prior to randomization.
- 17. Subject has clinically significant abnormalities in clinical chemistry, hematology or urinalysis, including aspartate aminotransferase (AST) or alanine aminotransferase (ALT) or bilirubin (unless known diagnosis of Gilbert's syndrome) ≥ 3.0 times the upper limit of the reference range or a serum creatinine > 2.0 mg/dL at Screening. Clinically significant laboratory abnormalities may be retested 1 time prior to

- Day 1; however, the results must meet entry criteria prior to study drug administration on Day 1.

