- HDL-C: < 40 and ≥ 40 mg/dL
- LDL-C: < 130 , $\geq 130 - < 160$, $\geq 160 - < 190$, and ≥ 190 mg/dL
- TG: ≤ 150 , $> 150 - \leq 300$, $> 300 - \leq 500$, $> 500 - \leq 1000$, and > 1000 mg/dL
- LDL-C/HDL-C ratio: ≤ 3 , and > 3
- Total cholesterol/HDL-C ratio: ≤ 4.5 , and > 4.5

In addition, the number and percentage of subjects who have potentially clinically significant (PCS) lipid values meeting the following criteria any time during the appropriate Treatment Period will be summarized by treatment group. Listings will be provided to summarize subject-level laboratory data for subjects meeting PCS criteria.

- Total cholesterol > 200 mg/dL
- LDL-C > 130 mg/dL
- LDL-C > 160 mg/dL
- HDL-C < 40 mg/dL
- TG > 150 mg/dL
- TG/HDL-C ratio > 3.5
- LDL-C/HDL-C ratio > 4

The following plots will be provided by treatment group for HDL-C, LDL-C, and triglycerides during the appropriate Treatment Period:

- Final post-baseline lab values vs. Baseline lab values
- Final post-baseline lab values vs. Baseline lab values for subjects with NCI CTC Grade 3 or 4

- Worst post-baseline lab values vs. Baseline lab values
- Worst post-baseline lab values vs. Baseline lab values for subjects with NCI CTC Grade 3 or 4
- Mean percent change from baseline in lipid parameters over time

In addition, plots of mean lab values over time during the Treatment Period will be provided for hemoglobin, total cholesterol, HDL-C, LDL-C, triglycerides, LDL-C/HDL-C ratio, ALT, AST, bilirubin, apolipoprotein A and apolipoprotein B.

The number and percentage of subjects in each treatment group with maximum on-treatment laboratory values meeting the following criteria compared to the upper limit of normal (ULN) during the appropriate Treatment Period will be summarized to assess potential hepatotoxicity.

- $ALT \geq 3 \times ULN$ and total bilirubin $\geq 2 \times ULN$
- $AST \geq 3 \times ULN$ and total bilirubin $\geq 2 \times ULN$
- ALT and $AST \geq 3 \times ULN$ and total bilirubin $\geq 2 \times ULN$
- $ALT \geq 3 \times ULN$ and total bilirubin $< 2 \times ULN$
- $AST \geq 3 \times ULN$ and total bilirubin $< 2 \times ULN$
- ALT and $AST \geq 3 \times ULN$ and total bilirubin $< 2 \times ULN$
- $ALT \geq 3 \times ULN$ and total bilirubin $\geq 1.5 \times ULN$
- $AST \geq 3 \times ULN$ and total bilirubin $\geq 1.5 \times ULN$
- ALT and $AST \geq 3 \times ULN$ and total bilirubin $\geq 1.5 \times ULN$
- $ALT \geq 3 \times ULN, \geq 5 \times ULN, \geq 10 \times ULN, \geq 20 \times ULN$

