9.4 Analysis of Vital Signs and Weights

Vital sign measurements of pulse rate, sitting systolic blood pressure, and sitting diastolic blood pressure will be summarized.

Each vital sign variable and weight will be summarized for all time points (starting with Baseline) with the number of non-missing observations, mean and standard deviation, median, minimum and maximum. Mean change from baseline to each applicable post-baseline visit will be summarized for each vital sign variable, with the number of observations, baseline mean, and visit mean. The change from baseline mean, standard error, and 95% confidence interval will be presented for the mean change from baseline within each treatment group and difference between each elagolix group and placebo.

The number and percentage of subjects who have potentially clinically significant (PCS) vital sign and weight values meeting the following criteria will be summarized by treatment group. All increase/decrease is calculated from Baseline to a post-baseline visit in the Treatment Period.

- Diastolic blood pressure
 - ≤ 50 mmHg and ≥ 15 mmHg decrease
 - > 90 mmHg and ≥ 15 mmHg increase
 - ≥ 100 mmHg
- Systolic blood pressure
 - ≤ 90 mmHg and ≥ 20 mmHg decrease

- ≥ 140 mmHg and ≥ 20 mmHg increase
- ≥ 160 mmHg
- Pulse rate
 - ≤ 45 bpm and ≥ 15 bpm decrease
 - > 100 bpm and ≥ 15 bpm increase
 - ≥ 120 bpm
- Weight
 - $\geq 5\%$ decrease
 - $\geq 7\%$ increase.

Listings will be provided to summarize subject-level vital sign and weight data for subjects meeting PCS criteria.

The number and percentage of subjects who had a sustained PCS vital sign and weight values will be summarized by treatment group and a listing of these subjects will be provided. A sustained PCS value is defined as 3 consecutive PCS values.

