Appendix B. Definition of Adverse Events of Special Interest (AESI)

Adverse Events of Special Interest (AESI) will be identified using the following search criteria:

Item of Safety Interest	Method of Surveillance
Hot flashes	Non-bone related hypoestrogenic effects CMQ
Bone mineral density loss	Osteoporosis/Osteopenia SMQ
Anemia	Cases are identified through the Non-Hemolytic and Non-Aplastic Anemias CMQ Haematopoietic erythropenia SMQ
Bone Fractures	Osteoporosis/Osteopenia SMQ
Rash and hypersensitivity reactions	Anaphylactic reaction SMQ Severe cutaneous adverse reactions SMQ Drug induced rash CMQ
Lipid abnormalities	Dyslipidemia SMQ
Uterine bleeding change	Female reproductive bleeds CMQ
Endometrial safety	Uterine and fallopian tube neoplasms, malignant and unspecified SMQ Reproductive Premalignant Disorders SMQ
Hypoestrogenic AEs (excluding hot flashes, BMD loss, and fractures)	Non-bone related hypoestrogenic effects CMQ
Spontaneous abortion	Termination of pregnancy and risk of abortion SMQ
Obstetrical complications (maternal and infant)	Pregnancy, labor, and delivery complications and risk factors (excluding abortions and stillbirths) SMQ
Psychiatric events	Depression and suicide/self-injury SMQ
Cardiovascular events	Cardiac arrhythmias SMQ, Cardiomyopathy SMQ, and Ischemic heart disease SMQ
Thromboembolic events	Embolic and thrombotic events SMQ
Elevated hepatic transaminases	Drug related hepatic disorders – comprehensive search SMQ Enhanced pharmacovigilance hepatic terms (elagolix product specific) PMQ

[figure not shown]

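### The any-time table of potentially clinically significant lipid values in SAP 9.3 has no baseline rule, so it mixes new with pre-existing abnormality; a new-onset row would be a cheap improvement

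*SAP*

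**What the plan says.** SAP 9.3 plans a table of "subjects who have potentially clinically significant (PCS) lipid values meeting the following criteria any time during the appropriate Treatment Period", by treatment group. The criteria are total cholesterol > 200, LDL-C > 130, LDL-C > 160, HDL-C < 40 and triglycerides (TG) > 150 mg/dL, a TG/HDL-C ratio > 3.5 and an LDL-C/HDL-C ratio > 4. Nothing is said about the baseline value. Protocol 8.1.7.3 adds only that "The number of subjects reaching potentially clinically significant levels will be summarized by treatment group".

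Neighbouring rules are explicit. For ALT, AST and bilirubin, SAP 9.3 says that a subject counts whatever her baseline value was. For vital signs and weight, SAP 9.4 attaches a change from baseline to 8 of its 11 criteria and explains that "All increase/decrease is calculated from Baseline to a post-baseline visit in the Treatment Period".

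SAP 9.3 also plans other lipid outputs:
- mean change from baseline with a 95% confidence interval, within group and for each elagolix group against placebo;
- shift tables from baseline to worst and final value, by NCI CTC grade or laboratory range;
- counts in lipid bands at baseline and each visit;
- plots of worst and final value against baseline for HDL-C, LDL-C and TG, and of mean percent change over time;
- listings of the women who meet a criterion.

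**The concern.** A table of women who meet a limit at any time on treatment is naturally read as a table of events on treatment. Here a woman who entered with a total cholesterol above 200 mg/dL and did not change at all is such an event. The laboratory exclusion (protocol 5.2.2) gives numeric limits for liver tests and creatinine but none for lipids, so these women can be randomized. The SAP is silent on lipids where it is explicit for liver tests and vital signs, so whoever programs the table must take the literal reading, which counts them.

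Two things are at stake. In the placebo-controlled year the pre-existing cases add about equally to both arms and make the arms look more alike in this table. In the 36 open-label months there is no control arm, and the percentage cannot be read as the frequency of new lipid abnormality.

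**Working it through.** **The plan's own figure.** The documents give no figure for the lipid counts. Their only design calculation is power above 90% for the co-primary endpoints with 400 against 200 women, two-sided 0.05 (protocol 8.2, SAP 2.4). A two-proportion normal-approximation calculation gives 99.4% for NMPP (54% against 35%) and more than 99.9% for DYS (59% against 23%), consistent with that statement. The same arm sizes and method are used below.

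**Step 1: what the other lipid tables supply at the same cut-offs.** The any-time criteria set against the bands of the baseline-and-visit table in SAP 9.3:

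| Any-time criterion | Nearest cut in the by-visit table | Baseline count available? |
|---|---|---|
| HDL-C < 40 | < 40 | yes |
| TG > 150 | > 150 | yes |
| LDL-C > 130 | ≥ 130 | nearly |
| LDL-C > 160 | ≥ 160 | nearly |
| Total cholesterol > 200 | lowest band ≤ 300 | no |
| LDL-C/HDL-C > 4 | 3 | no |
| TG/HDL-C > 3.5 | not listed | no |

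Four of seven criteria have a matching or nearly matching baseline count; three have none. Even for the four, the counts are marginal totals. Subtracting a baseline total from an any-time total does not give the number of new cases, because some women beyond the limit at baseline may have no such value later. The shift tables use other limits.

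**Step 2: size of the attenuation.** Let b be the share beyond the cut-off at baseline, s the chance that such a woman has a qualifying on-treatment value (taken as equal in both arms), and i0 and i1 the new-onset risks on placebo and on elagolix plus E2/NETA among the other women.

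- All-women rate = b·s + (1 − b)·i
- All-women risk difference = (1 − b)·(i1 − i0)

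The documents give no value for b, s, i0 or i1. The values below are assumptions, with s = 1.

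Worked line for b = 20%, new onset 10% against 5%: active 0.20 + 0.80 × 0.10 = 28.0%; placebo 0.20 + 0.80 × 0.05 = 24.0%; difference 4.0 points instead of 5.0; ratio 28.0/24.0 = 1.17 instead of 2.0.

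| New onset, active / placebo | b | All-women rates | Difference (points) | Ratio | Share of active-arm count that is pre-existing (b ÷ active rate) | Power, all women / at risk |
|---|---|---|---|---|---|---|
| 10% / 5% | 20% | 28.0% / 24.0% | 4.0 | 1.17 | 71% | 18% / 46% |
| 10% / 5% | 30% | 37.0% / 33.5% | 3.5 | 1.10 | 81% | 13% / 41% |
| 20% / 10% | 10% | 28.0% / 19.0% | 9.0 | 1.47 | 36% | 68% / 86% |
| 20% / 10% | 20% | 36.0% / 28.0% | 8.0 | 1.29 | 56% | 50% / 82% |
| 20% / 10% | 30% | 44.0% / 37.0% | 7.0 | 1.19 | 68% | 37% / 76% |
| 20% / 10% | 50% | 60.0% / 55.0% | 5.0 | 1.09 | 83% | 22% / 60% |

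The at-risk figures use 400(1 − b) against 200(1 − b) women. With s = 0.9 the risk differences are unchanged and the ratios hardly move (for 20% / 10%, b = 20%: 1.31). If s differed between arms, the difference would gain the term b·(s1 − s0) and the simple factor would no longer hold.

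**The case against.** The strongest reply is that this is one descriptive table among several. A reader might infer that the drug's lipid effect is diluted throughout the report. The documents do not support that: mean change against placebo covers all the lipid variables, including the two ratios, and the shift tables and plots keep the baseline reference. For HDL-C, TG and LDL-C the by-visit table already shows baseline prevalence by arm. All of this stands.

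Two other strong readings also fail. Randomization gives no reason to expect more pre-existing cases in one arm, so the table is attenuated, not biased in a direction. And the lipid adverse event of special interest in SAP Appendix B is found through the "Dyslipidemia SMQ" applied to adverse event terms; this laboratory table does not feed it.

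It can also be said that level-only counting is a convention in this SAP: the liver rule is explicit, and three vital-sign criteria (diastolic ≥ 100 mmHg, systolic ≥ 160 mmHg, pulse ≥ 120 bpm) need no change. That is fair, and the protocol's verb in 8.1.7.3 is too ordinary to settle the matter. But it argues for stating the rule for lipids, not for leaving it open.

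Entry is not wholly unguarded. Lipids are drawn at Screening, and the exclusion reads "Subject has clinically significant abnormalities in clinical chemistry, hematology or urinalysis"; protocol 5.3.1.1 also bars randomization when the investigator judges a screening result clinically significant. That may lower the prevalence, but it is a judgement and not a limit at these cut-offs.

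Finally, the ratio makes the loss look larger than the risk difference does: in the first example, 2.0 to 1.17 against 5.0 to 4.0 points. Both scales are shown for that reason.

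**Conclusion.** The point holds as a cheap improvement. The any-time lipid table counts women who were already beyond a cut-off at entry. Its risk difference is smaller than the new-onset difference by the factor 1 − b when those women are counted equally in both arms, and its ratio moves towards 1: from 2.00 to between 1.47 and 1.09 for b from 10% to 50% under the assumed 20% against 10%. In the open-label period the table cannot distinguish new from existing abnormality. Whether most of the count is pre-existing depends on the assumptions; in the table above that share runs from 36% to 83%.

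The remaining gap is specific. No planned table gives new-onset counts at these cut-offs, and three criteria (total cholesterol > 200, LDL-C/HDL-C > 4, TG/HDL-C > 3.5) have no baseline count at all. Prevalence and incidence are assumed throughout. The power figures only illustrate lost contrast, because SAP 9.3 names no test for this table and the protocol offers Fisher's exact test only as a general method for categorical safety data (8.1.7.1).

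**What to change.** In SAP 9.3:

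1. Keep the all-women any-time count.
2. For each of the seven criteria, add the baseline count by arm and a new-onset row. Denominator: women who do not meet the criterion at baseline and have a post-baseline value. Numerator: those of them who later meet it. A cross-tabulation of baseline against worst value at the same cut-offs would serve equally well. Baseline should be the one that SAP 9.1 defines for the period or analysis set being summarized.
3. State the baseline rule for lipids in one sentence, as the section already does for liver tests.

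The cost is SAP wording and a few extra rows from data already collected. The new-onset row has a smaller denominator, and it does not show worsening in women already beyond a limit. For that reason it should stand beside the all-women row and not replace it.
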